Study Protocol and Statistical Analysis Plan

Title: Effects of an exercise program for people with diabetic foot ulcers: A feasibility study with outcomes

Registration number: NCT03002155

Document date: Updated 2022-07-07

Aim of study:

This research aimed to address the concerning cycle of deconditioning and disablement in people with DFUs by introducing a seated exercise intervention to improve meaningful health and quality of life outcomes. We examined the feasibility of conducting a randomized controlled trial to assess the effects of 12-weeks of seated exercise in people with DFUs compared to peers who did not exercise. We also assessed physical, physiological, and psychosocial health outcomes in both groups. The exercise intervention in this study was EnhanceFitness,¹ an community-based group exercise program appropriate for people with weight-bearing restrictions due to wound-healing protocols. Numerous studies have been conducted that provide evidence of health benefits associated with participation in EnhanceFitness in older adults, including participants with diabetes.²⁻⁷ We hypothesized that people with DFU who engaged in the fitness program would report high levels of satisfaction, adherence and participation, and a low frequency of adverse events. We also hypothesized that participation in the exercise program would be associated with improvements in key health outcomes as compared to a standard-care control group, who were instructed not to engage in regular exercise (i.e., not to change their current habit of no regular exercise).

Materials and methods

A pilot randomized controlled trial was conducted. Study participants were randomly assigned to a group-based exercise program with a seated option for participation (the EnhanceFitness intervention, described below) or to the control group. Participants in the exercise group attended fitness classes for a 12-week period; those in the control group received standard care, which did

not include exercise. Both groups of participants were assessed at two time points, baseline and 12-week follow-up.

Participants

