Feasibility Outcomes. We assessed feasibility outcomes to inform future, large-scale RCT research in this area. The feasibility of conducting a RCT to assess effects of seated exercise in people with DFUs was evaluated using the following parameters: (1) recruitment and retention; (2) adherence to the exercise protocol; (3) participant satisfaction with the exercise program; and (4) presence of serious adverse events. Retention was quantified as the percent of participants that completed the study (i.e., attended both the baseline and 12-week follow up appointments), as well as percent of those who withdrew during the study or were lost to follow-up in each arm. Adherence was quantified as percent of exercise sessions attended by those randomized to the exercise group (out of 36 possible sessions). Satisfaction with EnhanceFitness was quantified as a continuous score on a measure of satisfaction, ranging from 0 (not at all satisfied) to 5 (very satisfied). Finally, presence of serious adverse events (SAEs: adverse outcomes, related or unrelated to the study, such as hospitalizations, emergency room visits, increase in wound size,

and infection, over the course of the study) was quantified as the total number of SAEs reported by participants in each trial arm.

Health Outcomes. We anticipated that exercise might affect many aspects of health and health-related quality of life in people with current or recently-healed DFUs. The following health outcomes were assessed: (1) glycated hemoglobin (HbA1c¹⁰); Five-times sit-to-stand test (5xSTS, a measure of lower extremity strength¹¹); Timed-up-and-go (TUG, a measure of functional mobility¹²); and 30-second biceps curls (a measure of upper extremity strength). We also asked participants to complete a survey comprised of standardized self-reported health measures, including the Patient-reported Outcome Measurement Information System measures of global health (PROMIS-Global 10-item short form),¹³ depression (PROMIS-Depression 4-item short form),¹⁴ fatigue (PROMIS-Fatigue 8-item short form), and physical function (PROMIS-Physical Function 11-item short form).¹⁵ The Activities-Specific Balance Confidence Scale was used to assess balance confidence.¹⁶

Additional variables. Participant characteristics (e.g., age, sex, body-mass index, duration of diabetes) were collected at baseline to characterize the sample and evaluate the comparability between the exercise and control groups.

Procedures

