12-week data collection session. At the 12-week session, we administered a follow-up survey to assess changes in the previously listed self-reported health outcomes. The survey also included questions to assess satisfaction with the EnhanceFitness intervention for participants in the exercise group. Following the survey, we asked participants to perform the 5xSTS, TUG, and biceps curls. At the end of the session, the participant returned to the laboratory to have their blood drawn and tested for HbA1c.

Analysis

Sample Characteristics. Descriptive statistics (mean, standard deviation, frequency distributions) were calculated for variables used to characterize the sample (e.g., participant characteristics). Student *t*-tests (numeric data) and Chi-square tests (nominal data) were used to compare the intervention and control groups based on participant characteristics. The alpha level for these tests was set at $\alpha=0.05$ and significant findings for sample variables indicate that there are differences in demographic or clinical characteristics (e.g., age, sex, duration of diabetes) between the exercise and control groups.

Feasibility Outcomes. The ability to meet recruitment targets (20 participants per group, 40 total) was assessed. Retention (or percent of participants that completed the study) and percent attrition was calculated and reported separately for the intervention and control groups. Pre-intervention

characteristics were compared between participants who did and did not complete the study to determine if there was a biasing effect. Adherence to the protocol was assessed in the intervention group to quantify the extent to which participants attended exercise classes. Satisfaction with EnhanceFitness was assessed in the intervention group to ensure that participants reported a minimum of 4 on a 5-scale measure of satisfaction with the exercise intervention.

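### Serious adverse events are summarised only as an event total per arm, which from two events upward does not identify how many participants were affected

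*Combined protocol and SAP*

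**What the plan says.** The Aim of study section gives the hypothesis as follows: "people with DFU who engaged in the fitness program would report high levels of satisfaction, adherence and participation, and a low frequency of adverse events". Under Outcomes, Feasibility Outcomes, the stated purpose is: "We assessed feasibility outcomes to inform future, large-scale RCT research in this area". The last of the four parameters listed there is "4) presence of serious adverse events".

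The same paragraph defines the parameter as "presence of serious adverse events (SAEs: adverse outcomes, related or unrelated to the study, such as hospitalizations, emergency room visits, increase in wound size", with infection added as a further example, over the whole study period. It then states the measure: it "was quantified as the total number of SAEs reported by participants in each trial arm".

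Under Analysis, Feasibility Outcomes, the plan covers recruitment ("The ability to meet recruitment targets (20 participants per group, 40 total) was assessed"), retention ("Retention (or percent of participants that completed the study) and percent attrition was calculated and reported separately for the intervention and control groups"), adherence and satisfaction. SAEs do not appear there. The Health Outcomes analysis deals with other variables. No section asks for the number or percent of participants who had an SAE, and none says how repeated or overlapping events in one person are counted.

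**The concern.** Presence is a yes/no property of a participant, whereas a sum of events is not. The two agree only when nobody has more than one event. The definition makes that hard to rely on, because the listed items can be successive stages of one illness. An infected ulcer that enlarges and leads to an emergency visit and then an admission could supply all four examples from a single person.

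A team planning the larger trial would want to know what share of people with diabetic foot ulcers had an SAE over 12 weeks. The planned summary does not give that share once an arm has two or more events. With about 20 people per arm, one participant with repeated events can make up most of the total, and a reader could not tell this from several participants with one event each.

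Retention, in the same paragraph, is expressed as a percent of participants, so person-level reporting is already part of this plan.

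**Working it through.** **Inputs.** The arm size is n = 20, the recruitment target under Analysis, Feasibility Outcomes. The documents give no SAE rate, threshold or expected count, so there is no planned figure to reproduce, and every event total k below is assumed. Follow-up is taken as complete, so nothing here depends on dropout.

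**Step 1: what a total implies about people.** If an arm has k events, the number of participants with at least one event lies between min(k, 1) and min(k, n). The lower limit applies when one person has all the events, the upper limit when every event is in a different person.

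| Assumed total k | Participants affected | Percent of 20 |
|---|---|---|
| 0 | 0 | 0% |
| 1 | 1 | 5% |
| 2 | 1 to 2 | 5% to 10% |
| 4 | 1 to 4 | 5% to 20% |
| 5 | 1 to 5 | 5% to 25% |
| 6 | 1 to 6 | 5% to 30% |
| 10 | 1 to 10 | 5% to 50% |

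Totals of 0 and 1 identify the number affected. Totals of 2 or more do not.

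**Step 2: what the planned reporting does supply.** Recruitment and retention by arm give a denominator, so events per randomised participant can be derived. For k = 5 this is 5/20 = 0.25. It is 0.25 whether one person or five people were affected, so the denominator does not resolve the ambiguity.

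**Step 3: the proportion at the two ends for k = 5.** Exact (Clopper-Pearson) 95% limits for x affected out of n are the 0.025 quantile of Beta(x, n − x + 1) and the 0.975 quantile of Beta(x + 1, n − x).

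- x = 1: 1/20 = 5%; Beta(1, 20) and Beta(2, 19) give 0.1% to 24.9%.
- x = 5: 5/20 = 25%; Beta(5, 16) and Beta(6, 15) give 8.7% to 49.1%.

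The same total is thus compatible with point estimates that differ fivefold. The uncertainty from not knowing x comes on top of the sampling uncertainty in each interval.

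**The case against.** The strongest reply is that an event total is a legitimate safety summary. The hypothesis speaks of frequency without giving a unit, and events over a known denominator is one fair reading of that word. This stands: the total is not wrong and should be kept. What it does not do is measure presence, which is the parameter the plan names.

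A second reply is that the person count can be produced from the raw data, because the SAEs came from participants' own reports. That may well be so, although the documents do not state that each event is linked to a participant. It makes the change cheap, but it does not put the summary into the plan.

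A third reply is that this is a pilot of 40 people with no planned inference on SAEs, written largely in the past tense, so the change may amount to a reporting addition. That also stands, and it limits the weight of the point.

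Two stronger readings are tempting. A reader might infer that the plan can never show how many people had an SAE. That goes too far: totals of 0 or 1 do show it, and the underlying reports may contain it. A reader might also infer that the totals could rank the exercise and control arms wrongly. The documents do not support building on that. The hypothesis concerns people who took part in the program, no SAE test or ranking of arms is specified, and any reversal would have to be constructed from assumed totals and extreme clustering.

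**Conclusion.** The point holds as an incomplete descriptive summary, not as an invalid analysis. The named parameter is presence, the only specified measure is an event total, and no other section supplies a participant-level count.

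Its size depends on the data. There is no ambiguity at 0 or 1 event in an arm. At an assumed 5 events among 20, the share affected can be anywhere from 5% to 25%. If every event happened to fall in a different person, the total would equal the number affected, but the total alone would not tell the reader so.

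The conclusion rests on the target arm size of 20 and on the definition allowing one person to contribute more than one event, which nothing in the plan rules out. It does not rest on any assumption about dropout; the documents establish neither the size nor the direction of an effect of dropout on the SAE count. It supports no claim about relative safety between arms.

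**What to change.** Add one sentence to the Feasibility Outcomes part of the Analysis section: for each arm, report the number and percent of randomised participants with at least one SAE, with an exact 95% confidence interval, as the measure of presence, and give the total number of events beside it. The person count is unaffected by how many times a single episode is counted, which is why it should carry the parameter. The total remains useful as a measure of burden.

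The cost is a few table rows. No new data collection is needed if each SAE can be traced to a participant; this should be confirmed, since the documents suggest it but do not say so. The drawback is precision. At 20 per arm even one affected participant gives an interval of 0.1% to 24.9%, so the figures should be presented as description for planning the larger trial and not as a between-arm safety conclusion.

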Participants (target n=40) were enrolled and randomly assigned to either the intervention or control group. A randomization schedule was created using random number generator in Microsoft Excel (Microsoft Corporation, Redmond, USA). The study research coordinator created the randomization schedule for 40 potential participants prior to any study enrollment. Group assignment was placed in sealed envelopes to blind study investigators to randomization allocation. Corresponding envelopes were not opened until the participant was enrolled into the study.

Eligibility criteria for this study included: (1) 18 or more years of age, (2) diagnosis of diabetes, (3) current or recently-healed DFU (in the last six months), (4) and able to attend regular exercise classes and two data collection sessions. Exclusion criteria included: (1) medical conditions where aerobic or resistance exercise was contraindicated⁸ (e.g., uncontrolled cardiovascular problems), (2) a score of less than 18 on the Montreal Cognitive Assessment indicating moderate cognitive impairment,⁹ (3) response from primary physician requesting that the participant not engage in exercise, (4) current participation in a regular exercise program (more than 30 minutes, more than 2 times a week).

Study participants were recruited from podiatry and wound care clinics in the metro area using posted recruitment materials. Potential participants were also identified through targeted

mailings to patients in the University of Washington medical system with ICD-10 codes that indicate the presence of a DFU. Interested patients were screened by telephone for initial eligibility and, if eligible to participate, were enrolled and randomized to either the exercise group or the control group. For those randomized to the exercise group, we sent a letter to each participant's primary physician to inform them of participation in the EnhanceFitness program. Physicians were asked to respond if their patient should not engage in moderate, non-weight bearing exercise. Informed consent was obtained from all participants prior to their involvement in the study.

Outcomes

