Participants were asked to come to the University of Washington for two data collection sessions. All study procedures were reviewed and approved by a University of Washington institutional review board (IRB). The study was also registered with clinicaltrials.gov

(registration number NCT03002155). Participants were compensated for their time and participation in the study.

Exercise intervention. EnhanceFitness, an existing, evidence-based exercise program, was the intervention for this study. These group classes were offered at no cost to participants. EnhanceFitness classes were designed specifically for older adults at all fitness levels and may be performed in a seated position. Classes were offered at multiple locations across the Seattle metropolitan region, including community and senior centers, making them a convenient option for participants in the study. Each hour-long EnhanceFitness class incorporated cardiovascular exercise (20 minutes), strength training (20 minutes), and stretching (10 minutes). Evidence suggests that EnhanceFitness improves strength,⁷ and reduces depression³ and falls⁵ in older adults. Participants in the exercise group attended EnhanceFitness classes three times a week for 12 weeks and were contacted regularly to remind them to attend their classes.

Control. Participants in the control group were contacted regularly to remind them to not change their exercise habits (self-reported as less than 30 minutes of activity, less than 2 times a week) while enrolled in the study. They were asked not to start new exercise regimens, or begin a regular exercise program. Any changes in their exercise routines were noted by researchers.

Baseline data collection session. At the baseline session, a study investigator explained the study to participants and obtained informed consent. We then administered a baseline survey and obtained performance measurements. The baseline survey included all self-reported health outcomes as well as demographic and health questions. Following the baseline survey, we

administered the 5xSTS, TUG, and biceps curls to assess each participant's baseline strength and mobility. At the end of the session, participants went to a hospital-based laboratory to have their blood drawn to test for HbA1c.

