Health Outcomes. Descriptive statistics were calculated for all physical, physiological, and psychosocial outcomes. Separate repeated measures analyses of variance (ANOVA) were performed for each health outcome. The ANOVA models included two factors, each with two levels (group: intervention, control; time: pre-intervention, post-intervention). The alpha level was set at $\alpha=0.10$ for health outcomes and was not adjusted for multiple comparisons. A less conservative statistical approach is warranted for this pilot study so that effects of the intervention could be recognized and, if results suggested that the intervention was beneficial, the results could be used to power and inform a larger RCT. Significant interactions of group x time (with corresponding evidence of improved outcomes in the intervention group) would indicate that the exercise program improved physical, physiological, and psychosocial outcomes in the exercise group compared to the control group.

References

8. Dugan JA. Exercise recommendations for patients with type 2 diabetes. *Jaapa*. 2016;29(1):13-8.

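### The two-visit repeated-measures ANOVA is a change-score t-test: valid, but usually less precise than ANCOVA on baseline values already collected

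*Combined protocol and SAP*

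**What the plan says.** The Health Outcomes paragraph of the Analysis section states that "Separate repeated measures analyses of variance (ANOVA) were performed for each health outcome". It describes the model as follows: "The ANOVA models included two factors, each with two levels (group: intervention, control; time: pre-intervention, post-intervention"). A significant group-by-time interaction, with improvement in the exercise arm, is the evidence of benefit. Alpha is 0.10, unadjusted for multiplicity. No covariate is named. The paragraph justifies the relaxed alpha by the wish to recognise effects, so that "the results could be used to power and inform a larger RCT".

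The design is simple. Under Materials and methods, "Both groups of participants were assessed at two time points, baseline and 12-week follow-up". Under Participants, "Participants (target n=40) were enrolled and randomly assigned to either the intervention or control group".

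Every health outcome has a baseline value, according to the description of the baseline session under Procedures:

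- Self-report measures: "The baseline survey included all self-reported health outcomes as well as demographic and health questions".
- Performance tests: the team "administered the 5xSTS, TUG, and biceps curls to assess each participant's baseline strength and mobility".
- Glycaemic control: "participants went to a hospital-based laboratory to have their blood drawn to test for HbA1c".

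**The concern.** With two arms and two visits, the interaction contrast is the difference between arms in mean change. Testing it is the same as a t-test on change scores, which subtracts the whole baseline value from the follow-up value. When the slope of follow-up on baseline is below 1, as it must be if the SDs are equal and the correlation is below 1, full subtraction over-corrects and adds noise. ANCOVA estimates the slope and removes only the part of baseline that predicts follow-up.

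The stake is precision. The plan accepts a higher false-positive rate to gain sensitivity in a sample of 40, while baseline adjustment can add sensitivity at the nominal error rate. The plan also wants figures to size a larger trial, but does not ask for the residual SD or the pre-post correlation, which a baseline-adjusted trial would need.

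**Working it through.** **Inputs from the documents.** Target 20 per group, 40 total (Analysis, Feasibility Outcomes); two visits; alpha 0.10, taken as two-sided because the interaction F-test has one numerator degree of freedom. The plan states no power, effect size, SD or correlation, so it has no figure of its own to reproduce.

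**Assumptions.** True difference 0.5 SD; pre-post correlation ρ from 0.5 to 0.95; equal SDs at both visits, then relaxed; 20 or 16 completers per arm.

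**Step 1: equivalence.** On simulated data the interaction F equals the squared change-score t: 1.0663 for both with 20/20 (p = 0.308), and 0.4888 for both with 17/14 (p = 0.490).

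**Step 2: variances, equal SDs (σ = 1).**

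- Change score: 2(1−ρ).
- ANCOVA: 1−ρ².
- Ratio: (1−ρ²)/[2(1−ρ)] = (1+ρ)/2.
- Estimating the slope multiplies the ANCOVA variance by 1+1/(N−4) on average. For N = 40 this is 1+1/36 = 1.028.

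At ρ = 0.5 the ratio is 0.75 × 1.028 = 0.771. ANCOVA on 40 therefore has the precision of the planned test on about 40/0.771 ≈ 52. At ρ = 0.95 it is 0.975 × 1.028 = 1.002, so there is no gain.

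Setting the ratio to 1 gives a break-even of ρ = 2(N−4)/(N−3) − 1:

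- N = 40: 72/37 − 1 = 0.946.
- N = 32: 56/29 − 1 = 0.931.

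**Step 3: power.** The change score uses a noncentral t with 2n−2 df. ANCOVA uses 2n−3 df, averaged over chance baseline imbalance.

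| ρ | Variance ratio (N = 40) | 20 per arm: planned / ANCOVA | 16 per arm: planned / ANCOVA |
|---|---|---|---|
| 0.5 | 0.771 | 46% / 55% | 40% / 47% |
| 0.6 | 0.822 | 54% / 61% | 46% / 52% |
| 0.7 | 0.874 | 64% / 69% | 56% / 60% |
| 0.8 | 0.925 | 79% / 82% | 71% / 73% |
| 0.9 | 0.976 | 97% / 97% | 93% / 93% |

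The 90% CI half-width at 20 per arm is 0.53 against 0.47 SD at ρ = 0.5, 0.41 against 0.39 at 0.7, and 0.337 against 0.325 at 0.8. At ρ = 0.5 the difference detectable with 80% power is 0.80 against 0.70 SD.

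Simulation with 40,000 trials per cell at 20 per arm agrees for ρ = 0.5 to 0.8 (for example 0.462 against 0.551 at ρ = 0.5). Simulated type I error is about 0.10 for both tests.

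**Step 4: unequal SDs.** With baseline SD s0 and follow-up SD s1, the change variance is s0² + s1² − 2ρ·s0·s1 and the ANCOVA variance is s1²(1−ρ²). The difference, before the small-sample term, is (s0 − ρ·s1)². It vanishes when ρ·s1 = s0, that is, when the slope is 1.

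Power for an effect of 0.5 baseline SD, 20 per arm:

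| s1/s0 | ρ | Change variance | ANCOVA variance | Planned / ANCOVA |
|---|---|---|---|---|
| 1.2 | 0.5 | 1.24 | 1.08 | 40% / 43% |
| 1.2 | 0.7 | 0.76 | 0.734 | 55% / 56% |
| 1.2 | 0.8 | 0.52 | 0.518 | 70% / 69% |
| 0.8 | 0.7 | 0.52 | 0.326 | 70% / 85% |

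**The case against.** The strongest reply is that nothing here is wrong. The planned test is an accepted one, the health outcomes are secondary to feasibility, and the gain depends on quantities the documents do not give. With equal SDs it falls to about 3 points at ρ = 0.8 and nothing at 0.9. At a true difference of 0.3 SD it is only 2 to 4 points for ρ of 0.5 to 0.8. All of that stands, and it limits the point to one of efficiency.

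Three further objections stand in part:

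- **Baseline timing.** The comparison needs baseline means that are equal in expectation. The Participants section describes enrolment and randomisation after telephone screening, while Procedures places consent and baseline measurement at a later-described session, so the order is unclear. If allocation could have affected baseline values or who supplied them, the two analyses may estimate different quantities. That is a separate issue, but the efficiency claim is conditional on it.
- **Planning figures.** The ANOVA error term gives the change SD. Together with the visit SDs, this largely recovers the correlation and residual SD. A trial analysed by change score would need only the change SD. So this part is a request to report the figures directly, not a claim that they are lost.
- **Two tests per outcome.** The plan is written in the past tense, so ANCOVA may come after the results. Under the null at 20 per arm, the chance that at least one of the two tests is significant at 0.10 is about 0.14 at ρ = 0.5 and 0.13 at 0.7. This is a reason to label the added analysis and not to choose between the two by p-value. It is no reason to leave the adjusted estimate out.

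**Conclusion.** The concern holds. The planned interaction test is the change-score t-test. It is valid and unbiased under randomisation with complete pairs, and usually less precise than ANCOVA. With equal SDs and a 0.5 SD effect, the loss at 20 per arm is about 9 power points at ρ = 0.5, 5 at 0.7, 3 at 0.8 and none from about 0.9. A larger follow-up SD usually shrinks the gain and can turn it into a slight loss; a smaller one enlarges it. Which case applies to each outcome cannot be read from the documents.

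This is an inexpensive improvement that serves both aims given in the Health Outcomes paragraph. It does not correct an error, and it changes no feasibility conclusion.

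**What to change.** For each health outcome, regress the 12-week value on arm and the baseline value of the same outcome, with participants in the arm to which they were randomised. Report the adjusted between-arm difference with its 90% CI, the residual SD and the pre-post correlation. A longitudinal model with a common baseline mean is a close alternative, though not an exact equivalent.

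If the ANOVA results already exist, keep them as the planned analysis and report the ANCOVA beside them as supplementary, labelled as added later. It should not replace them silently.

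The cost is one degree of freedom and one extra line of code per outcome, with no new data. ANCOVA on completers does not deal with dropout: like the two-visit ANOVA, it leaves out anyone without a 12-week value.

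### The repeated measures ANOVA compares change only among participants with both visits, so baseline-dependent loss in one arm biases the group x time contrast, and the planned completer comparison cannot establish whether bias occurred

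*Combined protocol and SAP*

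**What the plan says.** The design section fixes two assessments: "Both groups of participants were assessed at two time points, baseline and 12-week follow-up". Under Analysis, Health Outcomes, the method is "Separate repeated measures analyses of variance (ANOVA) were performed for each health outcome", and "The ANOVA models included two factors, each with two levels (group: intervention, control; time: pre-intervention, post-intervention"). The group x time interaction carries the conclusion, at alpha 0.10, which is set "for health outcomes and was not adjusted for multiple comparisons". The same paragraph says that the results could help to power a larger trial.

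On loss, Outcomes, Feasibility Outcomes counts the "percent of those who withdrew during the study or were lost to follow-up in each arm", and Analysis, Feasibility Outcomes reports retention and attrition by arm. That section also says that pre-intervention "characteristics were compared between participants who did and did not complete the study to determine if there was a biasing effect". This comparison is not described as split by arm.

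The document states no health-outcome analysis population, missing-data method or sensitivity analysis. It does not say in words that participants without a week-12 visit are left out. That follows from the method.

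**The concern.** With two time points, the interaction test in a 2 x 2 repeated measures ANOVA is the two-sample t-test on change scores. A participant without week 12 has no change score and contributes nothing. The contrast is therefore between returners in one arm and returners in the other.

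A change score is negatively correlated with its baseline when the pre/post correlation is below 1 and the SDs are similar. If the fitter exercise participants leave, those who remain start low and drift up, which looks like benefit. If the frailer leave, the reverse happens and benefit is hidden.

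One-arm loss is plausible from the design, although nothing forecasts it. Only the exercise arm has 36 sessions to attend, and the physician letter that may end participation is sent only for that arm.

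At stake is the health-outcome estimate. The plan would read a significant interaction as an effect of the program and might size the next trial from it. The plan also treats the completer comparison as able to settle whether there was bias.

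**Working it through.** The plan has no figure to reproduce: it gives no dropout rate, effect size or derivation of the sample size.

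**Inputs from the documents.** "recruitment targets (20 participants per group, 40 total"); two visits; alpha 0.10 for health outcomes. For comparing arms on characteristics, "The alpha level for these tests was set at $\alpha=0.05"; no level is stated for completers versus non-completers, so 0.05 two-sided is assumed there.

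**Assumed inputs.** Both visits normal with SD 1, higher values better; pre/post correlation ρ of 0.5 or 0.8; no true effect; 30% loss in the exercise arm by a logistic model on baseline with log-odds 1.0–1.5 per SD; 10% random loss in controls.

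**Step 1: bias of the change contrast.** With no effect, the expected week-12 value given baseline b is ρb, so expected change is −(1−ρ)b. If exercise-arm completers have mean baseline m and control completers have mean 0, bias = −(1−ρ)m. Integrating the dropout model with the fitter leaving gives m = −0.253 (log-odds 1.0) and −0.327 (log-odds 1.5).

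- ρ = 0.8: 0.2 × 0.253 = 0.051; 0.2 × 0.327 = 0.065 SD.
- ρ = 0.5: 0.5 × 0.253 = 0.126; 0.5 × 0.327 = 0.163 SD.

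Simulated trials of 20 per arm give about 0.05–0.07 and 0.12–0.17 SD. The sign reverses if the frailer leave.

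**Step 2: error rate.** About 14 and 18 completers remain. The SD of change is √(2(1−ρ)), so SE = √(2(1−ρ)) × √(1/14 + 1/18) = √(2(1−ρ)) × 0.356. This is 0.225 at ρ = 0.8 and 0.356 at ρ = 0.5. Two-sided 0.10 leaves 5% in the direction of benefit (z = 1.645).

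- Smallest bias: 0.051/0.225 = 0.23. P(Z > 1.645 − 0.23) is about 8% if the fitter leave; P(Z > 1.645 + 0.23) is about 3% if the frailer leave.
- Largest bias: 0.163/0.356 = 0.46. The corresponding values are about 12% and 2%.

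Simulation agrees with these ranges.

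**Step 3: power of the completer comparison for a baseline difference.** With k dropouts of 40 and standardised difference d, the noncentrality is d/√(1/k + 1/(40−k)), with 38 df and critical t = 2.024. Both d and k are assumed.

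| d | k = 4 | k = 8 | k = 12 |
|---|---|---|---|
| 0.3 | 8.6% | 11.5% | 13.5% |
| 0.5 | 15.2% | 23.4% | 29.2% |
| 0.8 | 31.6% | 50.5% | 61.8% |
| 1.0 | 45.6% | 69.3% | 80.6% |

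In the scenario of steps 1 and 2, the pooled comparison flagged the baseline difference in roughly 26–45% of simulated trials.

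**Step 4: loss driven by the course after baseline.** Here 20% are lost in each arm, ρ = 0.6, and there is no true effect. Exercise participants who do worse than their baseline predicts tend to leave (selection correlation 0.7); control loss is random. Over 6,000 trials the bias was +0.19 SD and false benefit 15.8% against about 5%. The completer comparison flagged 4.8%, its chance rate. The arms lost equal numbers, so attrition rates would show nothing either.

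**Step 5: what baseline adjustment does.** In the scenario of steps 1 and 2, ANCOVA on completers alone had bias of about 0.01 SD or less and a false-benefit rate of about 5%. Dropout in step 4 does not depend on baseline, so baseline adjustment cannot remove that bias.

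**The case against.** The strongest case against the point has four parts.

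- **The baseline-dependent bias is an adjustment problem.** Completer-only ANCOVA removes it without changing who is analysed. This stands. The mixed model is one of two adequate remedies for that bias, and participants with a baseline value only add little to the week-12 contrast.
- **The mixed model does not cure the harder case.** This also stands. If loss depends on the unobserved week-12 outcome, neither model corrects it. A reader might infer that including everyone with a baseline value restores the randomised comparison; it does so only if loss is unrelated to outcome given the observed data.
- **The dropout figures are assumptions, and false benefit needs the fitter to leave.** This is correct. Nothing in the documents says that the fitter would leave, so both directions are shown. A reader might also quote a single low power for the completer comparison, such as 17–29%. That holds only for d = 0.5 and 5–12 dropouts. The plan states neither, and the range over reasonable inputs is about 9–81%.
- **Attrition is reported by arm.** A reader might infer that the completer comparison is the only safeguard and that selective loss would pass unnoticed. The documents do not support that, because unequal rates would be visible. Different reasons behind equal rates would not be.

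This is also a 40-person feasibility pilot with deliberately lenient testing. That limits the weight of the point and argues against a full sensitivity analysis for every health outcome.

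**Conclusion.** The point holds in a limited form. The ANOVA is in effect an analysis of participants with both visits, and baseline-dependent loss in one arm biases it. Under the assumed 30% and 10% loss the bias is modest: about 0.05–0.07 SD at correlation 0.8 and 0.12–0.17 SD at 0.5, in a direction that depends on who leaves. These figures illustrate the risk; they do not show that the trial's results are biased.

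The claim that comparing baseline characteristics determines whether there was bias is not tenable at any sample size, because that comparison carries no information about a post-baseline course unrelated to baseline. This is a more basic weakness than its power.

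The consequence is confined to the health-outcome estimates and their use in planning a larger trial. Recruitment, retention, adherence, satisfaction and adverse-event counts do not depend on this model.

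**What to change.** 1. **Analysis, Health Outcomes.** Replace the ANOVA with a likelihood-based mixed model of both visits, with a common baseline mean and a group x week-12 term, including every randomised participant with a baseline value. State the assumption that loss is unrelated to outcome given the observed data.
2. **Analysis, Feasibility Outcomes.** Call the completer comparison descriptive, show it by arm with the reasons for dropout, and drop the claim that it determines bias.
3. **Optional.** For the outcomes that would be used to plan the larger trial, add a simple delta-adjusted analysis: shift the assumed week-12 values of exercise-arm dropouts in steps in the unfavourable direction and report where the conclusion changes. Only this step addresses loss that depends on the unobserved outcome.

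The cost is revised wording, an explicit missing-data assumption and a little more analysis. No new outcome measurements are needed.
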